5.4 Data Collection

The questionnaire (See Attachment 4- Patient Questionnaire and Researcher Documentation Form) will include the following questions prior to the use of the intervention:

- 1.) Using the visual analog scale provided how would you rate your pain the last time you remember having an IV inserted?
- 2.) Using a 0-5 Likert scale please rate how satisfied you were the last time you remember having an IV inserted?
- 3.) Do you think it is important to control the pain of starting an IV?

Once the IV has been placed the researcher will ask the patient the following questions:

- 1.) Using the same 0-10 pain scale how would you rate this IV insertion?
- 2.) Using the same 1-5 satisfaction scale how satisfied were you with this IV insertion?
- 3.) Would you choose to have a spray used again if you needed to have an IV inserted in the future?

The researcher will document the patient responses as well as the angiocatheter size, angiocatheter location, numbers of IV start attempts, the time that the intervention was applied and what interventional spray was used. (See Attachment 4- Patient Questionnaire and Researcher Documentation Form). This information will be coded and will be used to analyze study results post intervention. The presence of adverse events will be monitored and documented for 120 minutes following the IV insertion.

6.0 STUDY ADMINISTRATION

6.1 Description of Study Process

This study will be conducted using patients who are ordered to undergo a Nuclear Medicine Stress Test. These patients will only be seen in this department the day that the stress test exam is performed. The anticipated time it will take to gather the patient's information, conduct the recruitment and consent portion of the study is approximately 30 minutes per patient. This study will use a convenience sample of patients over a 4-month period. The target goal is 30 patients; however, researchers may recruit up to 80 patients.

Once the determination has been made by the researcher that the patient is a candidate for the study the patient has consented they will be assigned to either the control group or experimental group through a computerized randomization sheet. Both the control group and experimental group will be equally represented. Once the IV has been placed regardless of what intervention was used the patient will then be asked by the researcher the questions as stated above.

The participants will only have the intervention used on a first attempt IV access. If the participant has to have additional attempts by the researcher to start an IV, their study will automatically be excluded.

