4.0 SUBJECT ENROLLMENT

The study population for this research is a convenience sample of patients who have been ordered to undergo a Nuclear Medicine Stress Test at Aultman Hospital Heart Center. Upon arrival to the Nuclear Medicine department the patient must check in at the front desk for his/her scheduled exam. The patient will need to fill out the necessary documents required by the nuclear medicine department to perform the stress test imaging. In addition to the patient will be given a letter to make them aware that a research study is being conducted within the department. (See Attachment 1-Explanation of Research Study). This letter is only intended to inform the patient that a research study is being conducted this is not intended to be used for the consent process. When it is time for the patient's exam the researcher will take the patient back to the injection room where an explanation for the exam and need for IV access will be explained.

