6.2 Data Quality and Confidentiality

The information obtained during this study will remain confidential and will be stored in a file cabinet with a key lock. [name] and [name] the Sub- investigators of this study under the supervision of the Principle Investigator [name] will be responsible for the following:

- 1). Explaining the study to potential participants along with conducting the consent process with the patient.
- 2). Asking related questions to consented participants regarding the research information obtained during the conduction of this study.
- 3). The medical review of patient health information determine eligibility.
- 4). Administration of the vapocoolant spray and placebo spray prior to IV access.
- 5). Performing IV access on study participants
- 6). Identifying any adverse reaction to the intervention being used. All adverse events will be reported to and managed by the Principle Investigator.

These responsibilities performed only by the Sub Investigators will ensure that there will be no threat to the validity of the study being performed and its study results. Data for this study will be kept only as long as the study is being conducted and analyzed for results. Once this information has been obtained all records will be discarded in accordance with hospital policy and applicable regulations. Within the consenting process the patient will be made aware that their information will be kept confidential and that the patient has the right to end their participation in the study at any point.

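### The plan does not say who holds the randomization sheet or how upcoming assignments are concealed, and it does not require the baseline answers before assignment

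*Combined protocol and SAP*

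**What the plan says.** Allocation is described only in Section 6.1. The sequence begins "Once the determination has been made by the researcher that the patient is a candidate for the study the patient has consented", after which "they will be assigned to either the control group or experimental group through a computerized randomization sheet". The same section adds: "Both the control group and experimental group will be equally represented". It names no block size, no holder of the sheet and no concealment device. The attachments listed in Section 11.0 include no randomization procedure.

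Section 6.2 lists the sub-investigators' duties. Among them are "Explaining the study to potential participants along with conducting the consent process with the patient", "The medical review of patient health information determine eligibility" and "Administration of the vapocoolant spray and placebo spray prior to IV access", together with questioning participants and inserting the IV. It then states: "These responsibilities performed only by the Sub Investigators will ensure that there will be no threat to the validity of the study".

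On recruitment, Section 4.0 says: "The study population for this research is a convenience sample of patients". On blinding, Section 5.1 describes a single-blind study, and Section 5.3.1 masks the sprays from patients. On baseline, Section 5.4 places three questions before the spray is used, and Section 8.0 makes pre-procedure perception the covariate.

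**The concern.** Randomization protects a comparison only if the person deciding whether to enrol a patient cannot know or guess the next arm. Here the people who approach, screen and consent patients also treat them, and they have discretion. The sample is one of convenience, and under Section 4.0 the researcher judges language, literacy and capacity to decide. If the next arm were known, a visibly anxious patient could be approached or passed over differently according to arm, even without intent.

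The second risk concerns baseline. If the arm is already known when the researcher asks about the last IV, the prompting or recording of those answers may differ by arm. The answers then enter the analysis as the covariate, so adjustment could bring bias in. Baseline adjustment cannot reliably repair selection either, because current anxiety is not among the items that Section 5.4 records.

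**Working it through.** The point is procedural, so the main check sets the sections side by side.

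1. **Order of steps.** Section 6.1 gives eligibility, then consent, then assignment. This order protects enrolment only if the next assignment is neither visible nor predictable beforehand. No section secures that.
2. **Who does what.** Section 6.2 gives screening, consent, questioning, spraying and cannulation to the sub-investigators alone. Assignment is not on the list, and Section 6.1 puts it in the passive. The person who assigns is therefore unstated, and no independent person is named.
3. **Who knows past assignments.** The sub-investigators apply the spray (Section 6.2), and the researcher records which spray was used (Section 5.4). They know every earlier arm.
4. **Baseline against assignment.** Section 5.4 fixes baseline before the spray. Section 6.1 fixes assignment after consent. Neither orders baseline relative to assignment, so both of these sequences comply with the plan:
   - consent, baseline, assignment, spray;
   - consent, assignment, baseline, spray.
5. **Who rates.** Patients give their own ratings on the scales shown to them. The researcher asks and writes the answers down (Sections 5.2 and 5.4).

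One calculation bears on the design of the fix. The plan promises equal groups, and the operators know past assignments, so even a hidden list can be partly predictable if balance is forced in small blocks of known size. The plan gives no block size, so the sizes below are assumptions.

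- **Block of 2:** the first assignment is guessed with probability 1/2 and the second is certain. Correct guesses: (1/2 + 1)/2 = 75%. Known with certainty: 1/2 = 50%.
- **Block of 4:** the best-guess probabilities for the four positions are 1/2, 2/3, 2/3 and 1. Correct guesses: 2.833/4 = 71%. The third position is certain when the first two match (probability 1/3) and the fourth is always certain, so the share known with certainty is (1/3 + 1)/4 = 33%.
- **Block of 6:** by the same enumeration, 68% correct guesses and 25% certain.
- **Simple randomization:** 50% correct guesses and none certain.

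These figures measure how predictable the next assignment would be. They do not measure bias. They explain why the fix needs undisclosed, varying block sizes as well as a hidden list.

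**The case against.** The strongest reply is that the protocol is silent rather than wrong, and that several damaging readings go beyond the text. Four of these are tempting.

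- **A reader might infer that the sub-investigators make the assignments and can see the next line.** The first is plausible because no one else is given the task, but Section 6.1 is passive and the duty list in Section 6.2 omits it. A computerized sheet could be an open list, a one-at-a-time output, or a list held by someone else. The text supports only that foreknowledge is not prevented.
- **A reader might infer that assignment happens at consent, hence before baseline.** Section 6.1 says only that it follows consent. Attachment 4, the questionnaire form, is listed but its content is not in the text available, and it might settle the order.
- **A reader might infer that the researchers score the outcomes.** The patients do, without being able to identify the spray. An unblinded person recording their answers is a matter of blinding, which the plan openly declares as single, and concealment would not change it.
- **A reader might infer that patients with difficult veins would be steered.** That example is weak. Choosing the IV site belongs to the administration step in Section 5.3.3, and Section 6.1 excludes patients who need further attempts.

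It is also fair to say that a baseline recorded before assignment would adjust in part for steering on traits related to recalled pain or satisfaction. All of this narrows the point. What stands is that no section conceals upcoming assignments, no section places baseline before assignment, and Section 6.2 presents the concentration of roles as a safeguard.

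**Conclusion.** The concern holds in a limited form: a cheap improvement. As written, the plan can be followed to the letter while the enrolling staff know or can guess the next arm, or know it when they record the covariate. The assurance in Section 6.2 does not follow. Having a few people perform every step may help consistency, but it offers no protection against selection or arm-dependent recording when those people are unblinded.

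No numerical bias is offered. The share of enrolments affected, the difference in expected pain between the patients concerned and the outcome's standard deviation would all have to be assumed, because the documents give none of them. Nor do the documents show that foreknowledge would occur. The conclusion rests on the text available, and on reading the researcher of Sections 4.0 to 6.1 as one of the sub-investigators, as the exclusive duties in Section 6.2 imply.

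**What to change.** In Section 6.1, name a person who does not enrol patients to prepare the list in randomly varying blocks, with the sizes not disclosed to the sub-investigators. That person places the assignments in sequentially numbered, opaque, sealed envelopes. State that the next envelope is opened only after eligibility, signed consent and the three pre-procedure answers are on the form. Varying blocks still keep the groups close to equal wherever recruitment stops between 30 and 80.

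In Section 6.2, delete the statement that sole handling by the sub-investigators ensures validity.

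The preparer has to be found. The statistical assistance in Section 8.0 is described as help with data input and results, so it cannot be assumed to cover generating the list. The cost is up to 80 envelopes, a brief one-off task for a non-enrolling colleague and a short protocol edit. Sample size, visits and the intervention do not change. The operator remains unblinded, and the exclusion of patients needing more than one attempt is a separate matter that this change does not address.

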2.0 STUDY OBJECTIVES

2.1 Primary Objective

The Nuclear Medicine department at Aultman Hospital seeks to address the issue surrounding pain and satisfaction associated with the invasive procedure of starting an intravenous catheter (IV) for the injection of radiopharmaceutical

and/or medications needed to complete nuclear images and provide for viable scans. The primary purpose of this study is to determine if by applying a vapocoolant (cold spray) at the IV insertion site on Nuclear Medicine outpatients will increase the satisfaction with IV insertion as well as determine if pain of insertion is decreased. Furthermore, this study will examine the patients' perception in using a vapocoolant spray as a way to improve upon the traditional method of starting IV's that do not offer pain management prior to their insertion. A sterile water mist will be used as the comparator spray to add validity to the standard of care arm.

Research Questions:

For the purpose of this study, the following questions will be addressed:

1. Will patients perceive a vapocoolant spray to be more effective in reducing pain prior to IV cannulation insertion over saline spray?
2. Will the use of a vapocoolant spray increase satisfaction with insertion at an intravenous site over that of a sterile water spray?

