5.3.3 Intervention Administration

The researcher will access a peripheral IV site using the hospital protocol on inserting IV catheters. The researcher will select an IV site; the patient's skin will be cleansed prior to the intervention spray being applied per hospital protocol. The researcher will then spray the intervention spray made by the Gebauer Company according to the manufacturer's recommendations which is to spray the Ethyl Chloride aerosol can for 4 to 10 seconds from a distance of 3 to 9 inches (8-23 cm). Do not spray longer than 10 seconds. Spray the area for the time recommended or until the skin just turns white; do not frost the skin. With skin, taut, quickly introduce the needle because the numbing effect of ethyl chloride only lasts for a few seconds to a minute. (Gebauer's Ethyl Chloride Spray, 2016). Reapplication of the spray to the area when it has been too long or is no longer "numb" is also indicated by the manufacturer but for the purpose of this study the patient will only have the application applied once. For the control group the patient's skin will be prepared per hospital protocol then the researcher will apply the Nature's Tears Eye Mist to the area for 4-10 seconds prior to IV access.

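### Section 6.1 drops randomised, already sprayed participants who need a second IV attempt, so the comparison covers only first-attempt successes and is open to selection bias of unknown size and direction

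*Combined protocol and SAP*

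**What the plan says.** Section 6.1 assigns consenting, eligible participants to an arm from a computerised randomisation sheet, with the arms to be equal in size. On the spray it says: "The participants will only have the intervention used on a first attempt IV access". On repeat attempts: "If the participant has to have additional attempts by the researcher to start an IV, their study will automatically be excluded". It does not say whether the participant is withdrawn or only the data are set aside; either way the participant leaves the comparison.

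The outcome questions come after placement: "Once the IV has been placed regardless of what intervention was used the patient will then be asked". Section 5.4 has the same timing. It also has the researcher record the number of attempts and the spray used, and says of the recorded items: "This information will be coded and will be used to analyze study results post intervention". It specifies no report of attempts or exclusions by arm.

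Section 5.1 calls the study single blind, and Section 5.3.1 describes the sprays as unidentifiable by patients only. Under Section 6.2 the sub-investigators apply the spray, insert the IV and also have the task of "Asking related questions to consented participants regarding the research information obtained during the conduction of this study".

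Section 8.0 names a covariance analysis on pre-procedure perception and a minimum of 30 subjects, with up to 80 intended. It gives no analysis set, no sensitivity analysis and no allowance for exclusions.

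**The concern.** Randomisation makes the arms comparable at assignment. Here membership of the compared groups is settled later, by whether the first stick succeeds. That could depend on the spray, on the operator (who knows which spray was used) and on how difficult the patient's veins are. If failure rates differ by arm, or if different kinds of patient fail in each arm, the remaining groups are no longer the randomised ones.

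If pain rises with insertion difficulty, which is an assumption, the arm with more failures loses more of its painful insertions and looks better. Satisfaction is exposed in the same way. Even without bias, the result omits insertions that are probably the least comfortable, and the number analysed falls below the number randomised. Because no report of exclusions by arm is planned, a reader could not judge how far this had happened.

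**Working it through.** **Order of events.** Consent, randomisation, spray, first attempt, then exclusion if another attempt is needed (Sections 5.3.3 and 6.1). The exclusion is therefore always after randomisation and after exposure. No other section restores these participants.

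**Figures in the plan.** There is no first-attempt failure rate to reproduce. The only design figure is the minimum of 30, and this point does not depend on how it was obtained.

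**Loss of patients (failure rates assumed, equal arms).**
- 80 randomised, 15% v 25%: 40 × 0.15 = 6 and 40 × 0.25 = 10 excluded, leaving 64.
- 80 randomised, 10% v 30%: 40 × 0.10 = 4 and 40 × 0.30 = 12 excluded, leaving 64.
- 30 randomised, 20% overall: 30 × 0.80 = 24 left. Analysing 30 would need 30/0.80 = 37.5, so 38 randomised.

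**Size of a possible bias.** All inputs are assumptions; none comes from the documents.
- Pain SD: 2.5 points.
- Correlation ρ of pain with cannulation difficulty: 0.4 to 0.6.
- Loading L of first-attempt failure on difficulty: 0.4 to 0.8.
- No true spray effect on pain.

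Difficulty is standard normal, and an attempt fails when a standard normal score with loading L on difficulty exceeds the arm's quantile q. With failure rate f, mean pain among successes is shifted by −2.5 × L × ρ × m(f), where m(f) = φ(q)/(1 − f).

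m(f) is 0.195 at 10%, 0.274 at 15%, 0.350 at 20%, 0.424 at 25% and 0.497 at 30%.

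The false difference, unadjusted and favouring the arm with more failures, is 2.5 × L × ρ × (gap in m):

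| Failure rates | Gap in m | L=0.4, ρ=0.4 | L=0.8, ρ=0.6 |
|---|---|---|---|
| 15% v 20% | 0.076 | 0.03 | 0.09 |
| 15% v 25% | 0.149 | 0.06 | 0.18 |
| 10% v 30% | 0.302 | 0.12 | 0.36 |

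Adjusting for prior pain leaves these unchanged if prior pain is unrelated to difficulty. If that correlation is 0.4, then at L = 0.8 they become 0.04-0.08, 0.07-0.16 and 0.15-0.32.

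**Against sampling error.** At L = 0.8 and N=80 the adjusted standard error is 0.53-0.62 points. Simulated Type I error of a two-sided 5% test (also an assumption) is 4.9-5.3%, 5.1-6.2% and 5.8-9.2% for the three rows. A normal approximation agrees for the worst case: a bias of 0.36 over a standard error of 0.61 is a shift of about 0.6, and Φ(−1.36) + Φ(−2.56) ≈ 0.09. At N=30 the maximum is 6.3%.

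**Equal failure rates.** The bias is then zero only if the same kind of patient fails in both arms. At 20% in each, with L = 0.8 in one arm and 0.4 in the other, the difference is 2.5 × (0.8 − 0.4) × ρ × 0.350 = 0.14 to 0.21, favouring the arm with the higher loading. Nothing in the documents suggests such a contrast; it shows only that equal counts are not full protection.

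**What the fix does under the same model.** Analysing everyone on first-attempt ratings gives a difference within 0.01 of zero and 4.7-5.2% Type I error. That holds only if a failed stick does not itself worsen the rating. If it were rated 2 points worse (assumption), the difference against the arm with more failures would be 2 × (0.25 − 0.15) = 0.20 or 2 × (0.30 − 0.10) = 0.40.

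**The case against.** The rule has a sensible motive. Only the first attempt is sprayed, application is limited to one, and Section 5.3.3 reports that "the numbing effect of ethyl chloride only lasts for a few seconds to a minute". A rating taken after several sticks would mix in unsprayed ones. That stands, but it is a reason to tie the rating to the first attempt, not to remove the patient.

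The likely bias is small. Section 1.2 reports that vapocoolants are not expected to make cannulation harder, and Section 5.3.2 chills the control spray as well. Modest gaps leave the error rate close to nominal, and no section supports the threefold gap that reaches 9%. This also stands, and it limits the weight of the point.

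The fix is not free of difficulty. Ratings after a failed first attempt are not collected now. They would be asked by the unmasked operator, possibly between attempts, and the satisfaction item suits a failed stick less well. The baseline question, "how would you rate your pain the last time you remember having an IV inserted", also matches a failed stick less closely; that can cost precision but does not undermine the randomised comparison. If failure itself worsens ratings, the all-randomised difference includes any effect of the spray on first-attempt success as well as pain relief.

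A reader might infer that the rule favours the vapocoolant, or that operators would use it to shape the result. The documents support neither: they give no failure rates, the direction depends on which arm fails more often, and the absence of masking shows an opening, not conduct.

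**Conclusion.** The point holds as a structural weakness that should be fixed. The exclusion acts after randomisation and exposure, restricts the comparison to first-attempt successes, and reduces the analysed number with no allowance for it. The possible bias is of unknown size and direction. Under the assumptions shown it runs from about 0.03 to 0.36 pain points before adjustment, and Type I error departs clearly from 5% only at the widest gap. These ranges depend heavily on the assumed loading; halving it halves the unadjusted differences.

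It would go too far to conclude that the trial's result will be materially wrong, or that analysing all participants removes every difference unrelated to pain relief. The first needs failure rates the documents do not give. The second needs a failed stick to leave the rating unaffected. The main reason to change the plan is that the randomised comparison can be kept intact at little cost.

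**What to change.** 1. **Section 6.1:** replace the exclusion sentence with: 'All randomised participants are analysed in the arm assigned. Number of attempts and first-attempt success are reported by arm. An analysis limited to first-attempt successes is a sensitivity analysis.'
2. **Section 8.0:** add: 'The analysis set is all randomised participants in the arm assigned; participants with no rating are counted and reported by arm.'
3. **Sections 5.4 and 6.1:** ask the existing pain and satisfaction questions after the first attempt, successful or not. On the Attachment 4 form, define 'this IV insertion' as the first attempt made after the spray.

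The one-application rule is not touched and the pre-spray questions stay as they are.

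**Cost:** text edits in three sections and one line on the form. Attempts and spray used are already recorded. The questions do not change, but their timing does, and ratings after a failed first attempt become a new collection with the drawbacks noted above. The all-randomised result should therefore be read beside first-attempt success by arm and the sensitivity analysis.
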